**Subaim 1A. To determine if a compensatory increase in glucose stimulated insulin secretion (GSIS) by  $\beta$ -cells precedes PTDM development in patients without diabetes undergoing MRD HCT.** Based on our C-peptide and oral glucose tolerance test (OGTT) data, we hypothesize that PTDM-prone individuals maintain euglycemia pre-transplant via enhanced  $\beta$ -cell secretory capacity followed by progressive  $\beta$ -cell dysfunction and relative insulin insufficiency after transplant. In a prospective MRD HCT cohort without diabetes,  $\beta$ -cell function and secretory capacity will be directly measured with hyperglycemic clamps before and 90 days after transplant.

**Subaim 1B. To determine if excess glucagon secretion and impaired  $\alpha$ -cell response to glucose or GLP-1 contributes to the hyperglycemia of PTDM.** We will test the hypothesis that PTDM patients have increased glucagon levels and that glucose and GLP-1 induced  $\alpha$ -cell suppression are incomplete. To assess  $\alpha$ -cell dysregulation, glucose-induced glucagon suppression will be measured during a hyperglycemic clamp and during 2 OGTTs either with or without GLP-1 infusion, before and 90 days after HCT.

**Specific Aim 2. To determine if the IL-33/ST2 axis promotes immune/islet cell dysregulation during PTDM.** We hypothesize that PTDM is characterized by decreased protective IL-33/ST2 signaling in adipose tissue at rest (*i.e.* pre-transplant)

followed by increased systemic, inflammatory signaling during stress (*i.e.* post-transplant), which leads to  $\beta$ -cell compensation and exhaustion, respectively. To investigate the ST2 pathway, we will measure adipose and plasma levels of IL-33 and sST2 and quantify ST2 expression on circulating Tregs and Th1 cells before and after HCT from our MRD cohort. IL-33 effects on T cells and on human islet function will be assessed *in vitro*.

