### *Immune / Metabolic Studies*

In addition to the 6 study visits, this protocol will involve 5 separate blood draws for the patient [pre-transplant, Day +10, Day +20, Day +30, and Day +90 (all +/- 7 days)]. During each blood draw, no more than 50 ml of blood will be drawn for serum and lymphocyte analysis. Aliquots will be analyzed using standard immunologic techniques and by flow cytometry as outlined in the preliminary data section. Blood will be drawn for research purposes at the same time as routine blood sampling. Venous blood will be obtained by accessing the central venous catheter using sterile technique or via peripheral venipuncture. Samples will be coded with a unique alphanumeric identifier at the time of collection so that patient identity will be available only to study investigators and research staff. Codes will be sequential numbers and letters.

Blood samples and database will be maintained indefinitely by the study investigators or the laboratory of [name]/[name] and the research staff. A total of 250 ml of blood will be drawn on 5 occasions for lymphocyte and serum analysis.

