## 10.2 Statistical Analysis Plan

### *Primary analysis of Subaim 1A*

We will compare pre-transplant insulin secretion (first- and second-phase GSIS) among patients who do or do not go on to develop PTDM. Wilcoxon rank sum test will be applied to compare the population mean difference between these two groups.

Multivariable logistic regression will evaluate whether GSIS is an independent predictor of PTDM after adjusting for the following covariates: gender, conditioning (ablative vs. reduced intensity), or acute GVHD requiring steroids. The estimated OR and 95% CI of the OR will be provided to measure the effect of the association. We will take a similar approach for the primary analysis of Aims 1B and 2 which will compare post-transplant total glucagon secretion during the OGTT ( $AUC_{Glucagon0-120}$ ) and serum IL-33 levels among patients with or without PTDM, respectively.

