## Appendix A

### Study Table - Donor

	Baseline	Pre-Collection
Study Blood collection		X
Informed Consent	X	
Review of Eligibility	X	
Data Collection	X	X

Study Table - Patient

	Baseline	Pre-Transplant	Day 10 post-transplant	Day 20 post-transplant	Day 30 post-transplant	Day 80-100 post-transplant	D365 post-transplant	D730 post-transplant
Study Blood collection	X		X	X	X	X		
OGTT / Microdialysis - CRC visit		X				X		
OGTT / GLP-1 Infusion - CRC visit		X				X		
Hyperglycemic Clamp - CRC visit		X				X		
Informed Consent	X							
Review of Eligibility	X							
Data Collection	X	X	X	X	X	X	X	X

All dates for blood collection +/- 7 days, all dates for procedures / study visits +/- 10 days

Oral glucose tolerance testing and the hyperglycemic clamps will be performed on separate days as scheduling allows

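### The predictor-of-PTDM analyses can use IL-33 and glucagon values taken after diagnosis, and the Aim 2 primary names no draw among the four post-transplant ones

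*Combined protocol and SAP*

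**What the plan says.** In section 10.2, under the primary analysis of Subaim 1A, pre-transplant first- and second-phase GSIS is compared between PTDM groups by Wilcoxon rank-sum test. The text continues: "Multivariable logistic regression will evaluate whether GSIS is an independent predictor of PTDM after adjusting for the following covariates", namely gender, conditioning and acute GVHD requiring steroids. It adds that "The estimated OR and 95% CI of the OR will be provided to measure the effect of the association".

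The other two primaries get one sentence: "We will take a similar approach for the primary analysis of Aims 1B and 2 which will compare post-transplant total glucagon secretion" during the OGTT and "serum IL-33 levels among patients with or without PTDM, respectively".

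Timing comes from other sections:
- **Blood draws** (section 6.0, Immune / Metabolic Studies): "pre-transplant, Day +10, Day +20, Day +30, and Day +90 (all +/- 7 days".
- **Post-transplant OGTT** (section 6.0, OGTT): one window, day +80 to +100, with 10 days either side.
- **PTDM** (section 6.0, Diagnosis of PTDM): any qualifying glucose from day +1 to day +100.
- **Onset in the earlier cohort** (section 3.0): 50 of 84 patients, median day 23.

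Item 1 of the secondary analyses for Aim 2 asks whether pre- or post-transplant IL-33/sST2 levels predict PTDM. The general statistical plan tests at two-sided P<0.05 and states no multiplicity rule.

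**The concern.** For Subaim 1A the order in time is right: GSIS is measured before transplant and PTDM is counted afterwards. The same approach is then extended to values measured after transplant, while the outcome clock is already running. A value taken after diagnosis may be a consequence of PTDM, or of its treatment, as easily as a forerunner. Reporting it as an independent predictor would reverse the time order.

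The second problem is confined to Aim 2. Subaim 1A is fixed at the pre-transplant clamp and Subaim 1B at the single post-transplant OGTT window. IL-33 has four post-transplant draws, and neither a primary draw nor a summary over draws is named. The primary result could be chosen after the data are seen, and a difference at a late draw could then be called predictive.

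**Working it through.** **1. The plan's own figure.** Section 10.1, Aim 2: difference 70 pg/mL, SD about 70 pg/mL, 17 per group, two-sided 0.05, two-group t-test. The standardised difference is d = 70/70 = 1. Noncentral t gives 80.7% power at 17 v 17 (exact requirement 16.7 per group). The stated 80% is reproduced, for one comparison at 0.05.

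**2. How many cases precede each measurement.** Inputs: 50% incidence among 34 patients (section 10.1), so 0.5 × 34 = 17 cases; median onset day 23 (section 3.0), assumed to carry over. With 17 cases the median is the 9th, so 9 cases fall on or before day 23 and at most 17 − 9 = 8 remain afterwards.

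| Measurement | Window | Cases still undiagnosed |
|---|---|---|
| Day +10 draw (nominal day) | 3 to 17 | 9 to 17 |
| Day +20 draw (nominal day) | 13 to 27 | 9 to 17 |
| Day +30 draw | 23 to 37 | at most 8 |
| Day +90 draw | 83 to 97 | at most 8 |
| OGTT, day +80 to +100 | 70 to 110 | at most 8 |

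The windows follow from Appendix A: "All dates for blood collection +/- 7 days, all dates for procedures / study visits +/- 10 days". The earliest Day +30 draw is 30 − 7 = day 23, so at least 9 of 17 cases are diagnosed by then. A Day +20 draw can fall as late as day 27, and in that event at most 8 cases remain.

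**3. False-positive chance if all four post-transplant draws are tested at 0.05.** If independent: 1 − 0.95^4 = 18.5%. The draws come from the same patients, so independence is the upper figure. The documents give no between-draw correlation. Simulated rank-sum tests, 17 v 17, 20,000 trials per setting, equal correlation:

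| Assumed correlation | At least one P<0.05 |
|---|---|
| 0.3 | 17.2% |
| 0.5 | 15.6% |
| 0.7 | 13.3% |
| 0.9 | 9.5% |

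If all four were kept as primary with a Bonferroni level of 0.05/4 = 0.0125, power per draw at 17 v 17 would be 60.8%.

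**4. Power when prediction is limited to patients PTDM-free at the draw.** Two-group t-test, d = 1, two-sided 0.05, future cases against 17 non-cases:
- 17 v 17: 80.7%
- 9 v 17: 64.4%
- 8 v 17: 60.8%

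So power is 64.4% to 80.7% at nominal Day +10 or +20, and at most 60.8% at Day +30 or +90.

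**The case against.** **The carry-over of the logistic model is only one reading.** The sentence on Subaim 1B and Aim 2 says the values will be compared, and the odds ratio is described as measuring association. The secondary analyses for Subaims 1A and 1B reserve prediction for pre-transplant glucagon and OGTT results, and treat day +90 results as a comparison by established PTDM. This stands for glucagon: a reader might infer that the plan commits to day +90 glucagon as a predictor, and it does not say so. It stands less well for IL-33, because item 1 of the Aim 2 secondary analyses uses prediction for post-transplant levels outright.

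**The 18.5% is a ceiling.** The plan has no rule that any significant draw counts, and repeated draws in one patient are correlated. This is accepted. Even at an assumed correlation of 0.9, though, the chance is about twice the nominal level.

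**The draws may share one hypothesis.** Specific Aim 2 expects "We hypothesize that PTDM is characterized by decreased protective IL-33/ST2 signaling in adipose tissue at rest" before transplant, "followed by increased systemic, inflammatory signaling during stress" after it. That contrasts compartments and the periods before and after transplant. It does not show that Days +10, +20, +30 and +90 carry different hypotheses. This stands, but one prediction for all four draws still does not say which one decides the primary.

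**Two further inferences are not supported.** A reader might count the pre-transplant draw as a fifth candidate, but the word post-transplant reads most naturally over both glucagon and IL-33. A reader might also see a specimen conflict, because Specific Aim 2 mentions plasma. However, the Immune / Metabolic Studies section and section 10.2 both specify serum.

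**Conclusion.** The concern holds in two parts.

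**Timing.** Item 1 of the Aim 2 secondary analyses permits post-diagnosis IL-33/sST2 as predictors, and section 10.2 can be read as doing the same for primary IL-33 and glucagon. If the day 23 median applies, at least half of cases are diagnosed by the Day +30 and Day +90 draws and by the OGTT. Those values can show association with PTDM, not prediction of it.

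**Unnamed draw.** The Aim 2 power holds for one comparison that the plan does not identify. Testing all four draws at P<0.05 gives a false-positive chance of 9.5% to 17.2% over assumed correlations of 0.9 to 0.3, with 18.5% as the independent case.

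A reader might go further and infer that the sample size is wrong or that the Subaim 1B rank-sum comparison is invalid. Neither follows. The Aim 2 sample size reproduces, and comparing day +90 glucagon by PTDM status is a proper test of the hypothesis that PTDM patients have higher glucagon. The figures assume 17 cases and 17 non-cases, the earlier cohort's median, equal between-draw correlation and, for power, d = 1 among the remaining cases. This should be fixed before analysis.

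**What to change.** Amend section 10.2 in three places.

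(a) Use IL-33/sST2 as a predictor of PTDM only at a stated draw, in patients still PTDM-free on the actual date of that draw. Report later draws as association only, in all patients.

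(b) State that the logistic predictor model does not apply to day +90 glucagon. Keep the rank-sum comparison as the Subaim 1B primary. Base any claim of a new post-transplant change on the baseline-to-day +90 analysis by PTDM group already planned in the secondary analyses and the general statistical plan.

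(c) Before analysis, name one post-transplant serum draw as the Aim 2 primary and list the other three as secondary.

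The change is to wording only. The samples and diagnosis dates are already being collected, and the named-draw comparison keeps its 80.7% power. The cost falls on the predictor analysis, which has fewer cases: about 64% to 81% power at Day +10 or +20 and at most 61% later, under the assumptions above. Naming one draw also gives up primary status for the other three.

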### *Secondary analyses for Subaims 1A and 1B*

1) determining if glucagon secretion and OGTT results pre-transplant predict PTDM development (herein OGTT results refers to 2 hour blood glucose and peak/nadir/total hormone levels during OGTT), 2) determining if GLP-1 infusion increases insulin secretion and glucagon suppression compared to OGTT values without GLP-1, 3) comparing GSIS, glucagon suppression, and OGTT results at day +90 among patients with or without established PTDM, and 4) comparing the change in GSIS, glucagon suppression, and OGTT results at baseline to those determined at day +90 after transplant in the entire cohort or among groups stratified based on PTDM, conditioning regimen (ablative vs. reduced intensity) or for the presence or absence of acute GVHD treated with steroids.

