#### *Implications for $\beta$ -cell failure and $\alpha$ -cell dysregulation during PTDM development*

Glucose homeostasis is maintained by the coordinated secretion of insulin by pancreatic  $\beta$ -cells and glucagon by  $\alpha$ -cells (27, 28). In addition to blood glucose, this process is regulated by the gut-derived incretin hormones glucagon-like peptide-1 (GLP-1) and glucose-dependent insulinotropic polypeptide (GIP) which are secreted postprandially, promoting insulin release and glucagon suppression (29). In a prospective observational cohort study funded by the NHLBI a standard OGTT was performed on HCT recipients without established diabetes before and 90 days after transplant (Figure 1). Although insulin levels appear similar before and after transplant in the 2 groups, only in patients maintaining post-transplant euglycemia are  $\beta$ -cells able to prevent significant glucose excursions during the challenge (bottom panel B). Compared to pre-transplant values, blood sugars were elevated at all time points after HCT with no corresponding increase in insulin secretion by the PTDM group (top panel A). These data are most consistent with the development of a new  $\beta$ -cell defect after HCT.

Glucagon is secreted in response to hypoglycemia where it promotes hepatic glycogen breakdown and gluconeogenesis. Our preliminary data suggests that PTDM patients have elevated fasting and post-prandial glucagon levels when compared to their pre-transplant values and when compared to individuals maintaining euglycemia after HCT. This inappropriate glucagon elevation in PTDM patients exists despite factors known to inhibit  $\alpha$ -cells including elevations in blood glucose, insulin, and GLP-1 (Figure 1). Taken together these data indicate a role for hyperglucagonemia and impaired  $\alpha$ -cell regulation in PTDM

[figure not shown]
**Figure 1. OGTT suggests  $\beta$ -cell failure and impaired glucagon suppression during PTDM after HCT. Representative data from 8 HCT recipients without a pre-transplant diagnosis of diabetes is shown. Blood glucose, insulin, C-peptide, glucagon, and GLP-1 were measured every 30 minutes for 2 hours during a standard OGTT performed before and 90 days after HCT. Median values are depicted and data is stratified for the development of new-onset PTDM (A) or maintenance of euglycemia (B).**

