## **7.0 Risks and Toxicity Management**

### *Risks*

- 1) Study visits at Vanderbilt can be inconvenient
- 2) Venipuncture, blood sampling, and catheter insertion can cause mild discomfort, bruising, and rarely infection
- 3) Repeated blood sampling can worsen anemia, which is monitored frequently after transplant
- 4) Symptoms of hyperglycemia including: thirst, frequent urination, and dry mouth may develop during the hyperglycemic clamp. Symptoms will be monitored closely and minimized by keeping blood glucose levels at 200 mg/dL by adjusting the glucose infusion.
- 5) Arginine is a potent stimulator of insulin and glucagon secretion and will be used during the hyperglycemic clamp. Arginine is commonly employed as a diagnostic test for growth hormone deficiency. It may cause flushing, nausea, or vomiting in about 3% of subjects using doses 6 times the amount used in this study. Since arginine can cause vein irritation, it will be administered by a central venous catheter or large vein to minimize these symptoms.
- 6) GLP-1 [Clinalfa, Bachem (Weil am Rhein, Germany)] will be infused intravenously during the OGTT. GLP-1 can cause nausea, vomiting, headache, and hypoglycemia (usually in patients on combination therapy for diabetes). The dose of GLP-1 in this study is well tolerated and the hormone is rapidly metabolized with a half-life < 2 minutes in the circulation. Thus the effects of GLP-1 should be negligible shortly after stopping the infusion. Based on previous experience, GLP-1 should have no significant side effects at the dose given in this study.

For toxicity attributed to the study, the NCI Common Terminology Criteria for Adverse Events (CTCAE) version 5.0 will be used to characterize the severity.

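### Secondary OGTT analyses compare raw insulin and C-peptide without reference to glucose, so items 3 and 4 can be null despite a post-transplant β-cell defect, and the GLP-1 insulin contrast is probably biased toward zero

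*Combined protocol and SAP*

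**What the plan says.** Section 10.2, under the secondary analyses for Subaims 1A and 1B, lists four items. A parenthesis in item 1 fixes the meaning of the OGTT outcomes: "herein OGTT results refers to 2 hour blood glucose and peak/nadir/total hormone levels during OGTT". Items 3 and 4 use that term. Item 3 compares patients with and without PTDM at day +90, and item 4 compares the change from baseline to day +90. Item 2 is "determining if GLP-1 infusion increases insulin secretion and glucagon suppression compared to OGTT values without GLP-1". It speaks of OGTT values, so the parenthesis does not strictly govern it, but it too names no adjustment for glucose.

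Secretion indices are defined in section 6.0 (Calculations) for the clamp only. Glucose is not among the covariates of the primary logistic model, and the general statistical plan has no glucose-referenced hormone analysis.

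On the preliminary OGTTs, section 3.0 reports that "insulin levels appear similar before and after transplant in the 2 groups", while "blood sugars were elevated at all time points after HCT with no corresponding increase in insulin secretion by the PTDM group". It concludes: "These data are most consistent with the development of a new" β-cell defect after transplant. The basis is small: "Representative data from 8 HCT recipients without a pre-transplant diagnosis of diabetes is shown", shown as medians.

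**The concern.** In a clamp, glucose is fixed and insulin can be read directly. In an OGTT, glucose floats, and it is itself a stimulus to insulin. Two patients with the same insulin curve at different glucose levels do not have the same β-cell response. The sponsor reasons in this way in section 3.0, then plans to test insulin alone.

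Two consequences follow:

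- **Items 3 and 4.** The OGTT insulin and C-peptide comparisons can come out null on the very pattern that the preliminary data are said to show.
- **Item 2.** GLP-1 is infused throughout the second OGTT. Section 3.0 says that it promotes insulin release and suppresses glucagon, and that glucagon drives hepatic glucose output. If glucose is therefore lower in that test, the raw insulin contrast mixes the GLP-1 effect with a weaker glucose stimulus.

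**Working it through.** **Inputs from the documents.** The planned comparison is 17 versus 17, two-sided 0.05 (section 10.1). Preliminary insulin was similar and preliminary glucose was higher at all times after transplant in PTDM; no sizes are given and the figure is not available (section 3.0). Glucose and hormones are scheduled at the same 6 OGTT time points (section 6.0).

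**The plan's own figure.** For Subaim 1A, a difference of 7.5 with SD 7.5 and 17 per group gives 80.7% power by the noncentral t distribution. The stated 80% is reproduced and is not in dispute; it only sets the group sizes below.

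**Assumptions.** Insulin is taken as responsiveness × glucose. The glucose ratio r (PTDM to no PTDM) runs from 1.2 to 2.0. The log-scale SD runs from 0.3 to 0.6 and is taken as equal for the raw and the ratio measure. None of these sizes is in the documents.

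**1. When raw insulin hides a defect.** If responsiveness is reduced by a fraction f, the raw insulin ratio is (1 − f) × r. It equals 1 when r = 1/(1 − f):

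| f | Glucose ratio that hides it |
|---|---|
| 20% | 1.25 |
| 30% | 1.43 |
| 40% | 1.67 |
| 50% | 2.00 |

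Beyond that point raw insulin is higher in PTDM despite the defect: with f = 30% and r = 1.75, 0.70 × 1.75 = 1.22.

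**2. Power at 17 versus 17 when the raw insulin ratio is 1.0.** The raw comparison rejects in 5% of trials whatever r is. For log(insulin/glucose) the difference is log r and the noncentrality is log r / (SD × √(2/17)):

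| Glucose ratio | SD 0.3 | SD 0.4 | SD 0.5 | SD 0.6 |
|---|---|---|---|---|
| 1.2 | 40% | 25% | 18% | 14% |
| 1.5 | 97% | 82% | 63% | 48% |
| 1.75 | 100% | 98% | 89% | 75% |
| 2.0 | 100% | 100% | 97% | 90% |

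A Wilcoxon rank-sum simulation (20,000 runs) at r = 1.5 gives about 5% for raw insulin, and for the ratio 79% (SD 0.4) and 61% (SD 0.5). For item 4 the same arithmetic applies if r is read as the ratio of the two groups' glucose changes and SD as that of the log change.

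**3. GLP-1 contrast.** Let GLP-1 raise responsiveness by g. Treating the glucose fall d as a free quantity, the raw insulin ratio is (1 + g)(1 − d), which drops below 1 when d > g/(1 + g). But glucose also responds to insulin, so a feedback form is fairer: I = sG and G = R/(k + mI), where s is responsiveness and R is glucose appearance. Take k = 1 and R = 2 at baseline, with m from 0.2 to 5.

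- With R unchanged, a true rise of 50% shows as a raw rise of 26% to 38%, and a true rise of 100% as 48% to 71%. The effect is attenuated and keeps its sign.
- The raw ratio falls below 1 only if R itself drops by more than 33% (g = 50%) or 50% (g = 100%).
- The insulin-to-glucose ratio returns 1.5 and 2.0 throughout. This is by construction, because the model makes insulin proportional to glucose.

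**The case against.** The strongest objection is that the β-cell question does not depend on the OGTT. The clamp holds glucose at 200 mg/dL before and after transplant, second-phase GSIS is the Subaim 1A primary outcome, and items 3 and 4 compare GSIS beside the OGTT results. A null OGTT insulin result would be read next to it. This stands. A reader might infer that the trial would miss the defect, and the documents do not support that.

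Other parts that stand:

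- The OGTT definition includes 2-hour glucose, so the mismatch can be described informally from planned outcomes. What is missing is a pre-specified measure that combines the two.
- Item 1 is not shown to be affected. The glucose gap is reported after transplant only. Before transplant, Subaim 1A expects PTDM-prone patients to hold normal glucose through greater secretion.
- The preliminary statement reads mainly as before against after within each group, in 8 patients. It bears most directly on item 4. For item 3 a between-group insulin ratio near 1.0 is an extension of it.
- A reader might infer that the GLP-1 effect on insulin would change sign. In the feedback form with R, k and m unchanged, I = (R/G − k)/m, so lower glucose implies higher insulin. A reversal needs a large fall in glucose appearance not caused by insulin, and no figure for that is given. Section 7.0 does say that "GLP-1 can cause nausea, vomiting, headache, and hypoglycemia", but it adds that this is usually seen with combination diabetes therapy, so it is weak support in these patients.
- An insulin-to-glucose ratio ignores insulin sensitivity. The protocol expects insulin demand to rise, so resistance could raise the ratio and hide a defect in turn. That argues against making it the lead measure.

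What the objection does not remove is the missing OGTT index in items 3 and 4, or the exposure of item 2, since the clamp has no GLP-1 arm.

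**Conclusion.** The point holds, confined to insulin and C-peptide in secondary items 2 to 4. On the pattern in section 3.0, the raw OGTT insulin comparison has a chance of rejection near 5%. A glucose-referenced index would have power from 14% (glucose ratio 1.2, SD 0.6) to nearly 100% (ratio 2.0, SD 0.3 or 0.4). Those sizes are assumed; the direction rests on the sponsor's own description of 8 patients. Clamp GSIS limits the damage in items 3 and 4.

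For item 2 the supportable claim is attenuation toward zero, conditional on GLP-1 lowering glucose during the test. The documents give neither glucose values under GLP-1 nor a size for the effect.

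Glucagon is a different case. Higher glucose in PTDM should suppress it, so a raw glucagon excess in PTDM is conservative and the planned comparison is sound on this point.

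**What to change.** In section 10.2, pre-specify for items 2 to 4 the index log[AUC insulin(0–120)/AUC glucose(0–120)] and the same with C-peptide. Report both beside the raw levels, and interpret them in items 3 and 4 together with clamp GSIS. State that the ratio does not account for insulin sensitivity. Keep the raw glucagon comparisons as planned.

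For item 2, a mixed model of hormone on concurrent glucose may be added as a sensitivity analysis only. Glucose is itself affected by GLP-1, so conditioning on it does not cleanly isolate the GLP-1 effect.

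The cost is a derived index to define and a few more secondary comparisons. Glucose is already scheduled with every hormone sample, so no new blood, visits or patients are needed. Fixing the index before analysis also avoids choosing among indices after the data are seen.
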